EEG data will be recorded using a 64-channel TMS-compatible electrode cap (Easy Cap)¹². Signals will be collected at 2000Hz (impedance: $<5k\Omega$, low-pass filter: 0.1-500Hz) during preand post-TMS stimulation epochs (-100ms to 200ms) (Figure 3). Fifty suprathreshold (120% AMT) TMS pulses will be applied to M1 while the subject is seated quietly with eyes open^{13,14}. This procedure will be conducted bilaterally at each assessment timepoint (Pre-PAS, Post-PAS 0', Post-PAS 30', Post-PAS 60'). Peripheral auditory and somatosensory stimulation effects will be minimized to avoid EEG artifact¹⁵. Data epochs (-1000 to 4000 ms with respect to TMS delivery) will be extracted for subsequent imaginary phase coherence analysis (IPC). Post-TMS coherence values between electrodes overlying M1 bilaterally (C3 and C4) will be calculated within the beta frequency range (15 to 30 Hz)¹⁶. These IPC values will be used to index local M1 excitability and connectivity with the contralateral homotopic region^{17,18}. Differences in single-channel evoked potentials in the TMS alone will be calculated to consider the effect of afferent peripheral input on TMS-elicited cortical responses.

Figure 2. Example of TMS-evoked EEG data recorded from stimulated (iM1) and non-stimulated (cM1) cortical regions.

Motor function assessment:

In the stroke group, arm function will be evaluated by the Wolf Motor Function Test (WMFT), shown to be a valid and reliable test of arm function in stroke¹⁹. In both groups, hand-held dynamometry will be used to measure grip strength and manual dexterity will be indexed by the Nine-hole Peg Test (9HPT)²⁰. These assessments will be carried out by a licensed physical therapist ([name]) prior to completing the PAS protocol. The serial reaction time task (SRTT) will be performed at each assessment time point to evaluate motor skill performance. The SRTT involves pressing a key that corresponds to a target square positioned on a screen in front of the participant as quickly and accurately as possible. The response time for repeated and random sequences will evaluate SRTT performance.

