MRI acquisition: Scanning will be conducted at Emory University at the Center for Systems Imaging on a Siemens 3T Trio whole-body MRI scanner. A high-resolution T_1 scan (TR = 7.4ms, TE = 3.7ms, flip angle $\theta = 6^\circ$, FOV = 256mm, 160 slices, 1 mm thickness, scan time=3.2min) will be performed without contrast. The study team will have direct and immediate access to the data using Emory University's secure network server.

Statistical Plan:

To address the hypothesis that PAS induces LTP-like plasticity in both individuals with stroke and healthy controls, a three-way group (stroke, control) x condition (real PAS, sham PAS) x time (Pre-PAS, Post-PAS 0', Post-PAS 30', Post-PAS 60') analysis of variance (ANOVA) will be performed for the primary dependent measures (IPC and WMFT time). For the analysis, an alpha = .05 will be used and simple effects analyses will be performed for significant interaction effects.

Power analysis:

To ensure we have sufficient statistical power for our proposed aims, we used a combination of our standalone TMS data collected in participants with chronic stroke and TMS-EEG data collected to evaluate interhemispheric connectivity in young, healthy individuals¹⁶. To detect a hemispheric difference in iSP ratio of 0.06 with a common σ =0.11, b=0.8, a sample size of 27 subjects is required. In order to measure differences in TMS-evoked EEG responses in the hemisphere opposite the site of stimulation with a mean difference: 430µV.msec, common σ =288µV.msec, b=0.8, a sample size of 4 subjects is required. Due to the increased measurement variability in stroke, we chose a necessary sample size of n=30/group.

References:

Noninvasive brain stimulation to evaluate neural plasticity after stroke

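### For IPC, the planned ANOVA is valid but reads real versus sham PAS as change from Pre-PAS; adjusting for each session's own Pre-PAS IPC would be more precise at almost no cost

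*Combined protocol and SAP*

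**What the plan says.** The Statistical Plan states its aim as follows: "To address the hypothesis that PAS induces LTP-like plasticity in both individuals with stroke and healthy controls". The test is "a three-way group (stroke, control) x condition (real PAS, sham PAS) x time (Pre-PAS, Post-PAS 0', Post-PAS 30', Post-PAS 60') analysis of variance (ANOVA"), applied to the "primary dependent measures (IPC and WMFT time"). Pre-PAS is thus one of four levels of an outcome factor, "time (Pre-PAS, Post-PAS 0', Post-PAS 30', Post-PAS 60"), and no baseline covariate is named. On error control, "an alpha = .05 will be used", and "simple effects analyses will be performed for significant interaction effects".

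The section on EEG recording of TMS-evoked cortical responses says of the TMS-EEG measurement: "This procedure will be conducted bilaterally at each assessment timepoint (Pre-PAS, Post-PAS 0', Post-PAS 30', Post-PAS 60"). Every session that yields post-PAS IPC therefore has its own Pre-PAS IPC.

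The paragraph on PAS protocols assigns traditional PAS, ccPAS or sham by session, but also speaks of PAS groups. It does not settle whether real and sham are compared within or between participants. No random assignment, session order or counterbalancing is stated.

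**The concern.** Sham is the only comparator, so evidence that PAS does something must come from real versus sham after stimulation. In the planned model this is the condition x time interaction, with (2-1) x (4-1) = 3 degrees of freedom. Because the Pre-PAS means are left free in each condition, the interaction consists of differences in change from Pre. Each baseline is subtracted with a weight fixed at 1, whatever its actual correlation with the later values.

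The other routes to the effect also use the baseline poorly. The condition main effect averages in a time that precedes stimulation: a constant effect d at the three post-PAS times appears as (0 + 3d)/4 = 0.75d. A simple effect of condition at one post-PAS time gives the baseline a weight of 0.

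What is at stake is precision. The error bars on the PAS effect would be wider than the collected data require.

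**Working it through.** **1. The plan's own figures.** The Power analysis gives 27 subjects (iSP ratio difference 0.06, SD 0.11) and 4 subjects (difference 430, SD 288 µV.msec). With the one-sample or paired normal formula, two-sided alpha 0.05 and power 0.80, n = (SD x (1.960 + 0.842) / difference)²:

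- (0.11 x 2.802 / 0.06)² = 26.4, rounded up to 27
- (288 x 2.802 / 430)² = 3.5, rounded up to 4

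Both reproduce. Neither concerns real versus sham on IPC, and neither supplies an IPC variance or a pre-post correlation.

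**2. Direction of the loss.** Let b be the slope of post on Pre. If the expected Pre value is the same in real and sham, the variance of change exceeds that of the adjusted value by (1-b)² x Var(Pre). This is never negative, and it is zero only when b = 1.

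**3. Size of the loss.** Assume equal variance at all four times (set to 1) and a common correlation r. If participants receive both conditions, r refers to session-level deviations. If conditions are between participants, r is the pre-post correlation across participants. Each entry below is proportional to the variance of the real-versus-sham contrast.

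- One post-PAS time: change 2(1-r); adjusted 1-r²; ratio (1+r)/2
- Mean of three: change 4(1-r)/3; adjusted (1+2r)/3 - r² = (1-r)(1+3r)/3; ratio (1+3r)/4

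| assumed r | one time: change | adjusted | ratio | mean of three: change | adjusted | ratio | 30 x ratio |
|---|---|---|---|---|---|---|---|
| 0.2 | 1.600 | 0.960 | 0.600 | 1.067 | 0.427 | 0.400 | 12 |
| 0.3 | 1.400 | 0.910 | 0.650 | 0.933 | 0.443 | 0.475 | 14 |
| 0.5 | 1.000 | 0.750 | 0.750 | 0.667 | 0.417 | 0.625 | 19 |
| 0.7 | 0.600 | 0.510 | 0.850 | 0.400 | 0.310 | 0.775 | 23 |
| 0.9 | 0.200 | 0.190 | 0.950 | 0.133 | 0.123 | 0.925 | 28 |

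The last column is the approximate number who, analysed with adjustment, match 30 analysed as change on the mean of three. Against a simple effect at one post-PAS time, the ratio is 1-r²: 0.91, 0.75, 0.51 and 0.19 at r = 0.3, 0.5, 0.7 and 0.9.

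**4. Finite samples.** For 60 participants with two sessions and one post-PAS time, simulated variance ratios were 0.61, 0.70, 0.81 and 0.92 at r = 0.2, 0.4, 0.6 and 0.8. The formula gives 0.60, 0.70, 0.80 and 0.90.

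Power was also simulated (3,000 replicates) with 30 per condition, a constant effect at the three post-PAS times, and an effect sized for 80% nominal power on the 1-df change contrast:

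| assumed r | 3-df condition x time | 1-df change | mean post adjusted for Pre |
|---|---|---|---|
| 0.3 | 0.63 | 0.78 | 0.98 |
| 0.5 | 0.62 | 0.79 | 0.93 |
| 0.7 | 0.64 | 0.79 | 0.88 |
| 0.9 | 0.64 | 0.78 | 0.82 |

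The like-for-like comparison is between the last two columns. The gap to the 3-df test also reflects the choice of a 1-df average and the constant effect. In a within-participant version (n = 30), adjusted power at r = 0.9 was 0.78 and change 0.78, so the gain had almost gone. Simulated type I error was 0.04 to 0.06 for all the methods.

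**5. Which covariate.** If participants receive both conditions and the covariate is centred only within stroke and control, the slope blends between- and within-participant parts. In simulations with participant variance three times session variance, the saving for one post-PAS time was then about 17-19% at r = 0.2 and 4-5% at r = 0.8. The formula gives 40% and 10%. Adjustment still beat change in every scenario, but the covariate must be split to obtain the full gain.

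**The case against.** The strongest reply is that nothing here is an error. The ANOVA keeps its alpha under its assumptions, the study is a pilot, and change from Pre within real PAS is a natural reading of a hypothesis about inducing plasticity. That stands: the point concerns efficiency. A reader might infer that the planned test is invalid, and the documents do not support that.

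A second reply also stands. Having Pre-PAS as a time level is not the cause. The cause is leaving its means free by condition. A longitudinal model with four time levels and equal Pre-PAS means for real and sham recovers essentially the same precision.

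Third, the advantage assumes that real and sham have the same expected Pre-PAS IPC. Without it, change and adjustment can target different quantities, and centring within stroke and control does not help. The documents state no random assignment or session order, so the recommendation has to be conditional.

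Fourth, the size is unknown. A reader might infer from the power table that the study has about 63% power. It does not show that, because the effect size, the correlation and the constant effect are all assumed.

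Finally, a reader might extend the point to WMFT time, which the same sentence of the plan covers. The Motor function assessment section places WMFT in the stroke group only and before PAS is completed, so there is no post-PAS WMFT to adjust.

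**Conclusion.** The point holds for IPC as a loss of precision in a valid analysis. Its direction is firm whenever the expected Pre-PAS IPC is equal in real and sham: adjustment cannot have larger asymptotic variance than change. The size cannot be fixed from the documents. Under assumed compound symmetry and r from 0.2 to 0.9, the variance saved against change falls from about 40% to 5% for one post-PAS time and from about 60% to 7.5% for the mean of three. The small finite-sample loss nearly cancels the gain at the top of that range.

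The change is worth making because the baseline is already collected and the sample size was not derived from this contrast. It is a recommended improvement. The gain does not carry over to the comparison of stroke with control, which are not randomised groups and should not be equalised on baseline.

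**What to change.** In the Statistical Plan, for IPC:

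- State whether real and sham are compared within or between participants, and how condition or session order is assigned. Make the adjusted analysis conditional on that assignment being independent of Pre-PAS IPC.
- Model IPC at the three post-PAS times with that session's Pre-PAS IPC as covariate. If participants receive both conditions, enter two terms: the participant's mean Pre-PAS IPC and the session's deviation from it. If conditions are between participants, centre the covariate within stroke and control.
- Equivalently, keep four time levels in a longitudinal model with Pre-PAS means constrained equal across real and sham within each group.
- Use the adjusted model for the real-versus-sham contrasts only, and keep the four-level ANOVA as a sensitivity analysis.
- Decide separately, and in advance, whether the main contrast is a 1-df average over the post-PAS times or a multi-df test. The average favours sustained effects and is not required by this point.

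The cost is a few sentences of plan text, one or two degrees of freedom, and reliance on the equal-baseline assumption. No new data are needed.

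### WMFT time is a primary measure in a group x condition x time ANOVA, but it is collected only in the stroke group and only before PAS, so that analysis cannot be run

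*Combined protocol and SAP*

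**What the plan says.** The Statistical Plan specifies "a three-way group (stroke, control) x condition (real PAS, sham PAS) x time", with the time levels "Pre-PAS, Post-PAS 0', Post-PAS 30', Post-PAS 60') analysis of variance (ANOVA"), and states that this model "will be performed for the primary dependent measures (IPC and WMFT time"). The stated hypothesis is that PAS produces LTP-like plasticity in both stroke and control participants.

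The Motor function assessment section sets out who is tested and when:

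- **WMFT, who:** "In the stroke group, arm function will be evaluated by the Wolf Motor Function Test (WMFT").
- **Grip strength and 9HPT, who:** "In both groups, hand-held dynamometry will be used to measure grip strength and manual dexterity will be indexed by the Nine-hole Peg Test (9HPT").
- **When:** the next sentence says that these assessments are done "prior to completing the PAS protocol".
- **SRTT:** "The serial reaction time task (SRTT) will be performed at each assessment time point to evaluate motor skill performance".

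The section on EEG recording schedules the TMS-EEG procedure, from which IPC is derived, at all four time points. Nothing in the document schedules a WMFT in controls or a WMFT after PAS.

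**The concern.** A factorial ANOVA can estimate an effect only if the outcome is observed at more than one level of each factor involved. WMFT time is observed at one level of group (stroke) and one level of time (Pre-PAS). The model named for this primary measure therefore has no data for the contrasts it is meant to test. In particular, it has none for condition x time, which would show whether real PAS changes arm function relative to sham.

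One of the two primary measures then says nothing about PAS. If the text stays as it is, whoever analyses the trial will have to choose a different outcome, a different model or a different subset after the data are in. Meanwhile the motor measure that is scheduled at every time point, and is not restricted to the stroke group, is the SRTT, and the Statistical Plan does not mention it.

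**Working it through.** **The plan's own figures.** The only sample-size figures are in the Power analysis section. With a two-sided alpha of .05 and power 0.8 (z values 1.960 and 0.842), the paired normal formula n = (SD x (1.960 + 0.842) / difference)^2 gives:

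- iSP ratio: (0.11 x 2.802 / 0.06)^2 = 26.38, rounded up to 27, as stated.
- TMS-evoked EEG response: (288 x 2.802 / 430)^2 = 3.52, rounded up to 4, as stated.

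Both reproduce, but neither concerns WMFT time. No WMFT effect size or SD is given, so this section does not reveal an intended WMFT schedule. The point rests on the assessment schedule alone.

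**Cells required.** Group 2 x condition 2 x time 4 = 16. The full model has 3 main effects + 3 two-way interactions + 1 three-way interaction = 7 effects. With the intercept it has 1 + 1 + 1 + 3 + 1 + 3 + 3 + 3 = 16 parameters, and with all cells filled the design matrix has rank 16.

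**Cells available for WMFT time under each reading.**

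| Reading of the schedule | Filled cells | Empty cells | Rank | Effects lost (of 7) |
|---|---|---|---|---|
| Stroke only, Pre-PAS only (natural reading) | at most 2 | 14 | 2 | 6: group, time and all four interactions |
| Stroke only, all four times (loose reading of timing) | 8 | 8 | 8 | 4: group and its three interactions |
| Both groups, Pre-PAS only (WMFT assumed in controls) | 4 | 12 | 4 | 4: time and its three interactions |

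The second and third rows each relax one restriction. The three-way model fails in both, so either restriction alone is enough to defeat it.

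**What remains on the natural reading.** One contrast: real versus sham among stroke participants before that session's stimulation. It cannot contain an effect of that stimulation. It also needs both cells to be filled. If each person receives both conditions, that requires a WMFT at every PAS session, and the document does not say that the WMFT is repeated over the up to 5 sessions. If it is done once per person in such a design, even this contrast is lost.

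**The case against.** The strongest reply has four parts.

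1. **The timing rests on one loose sentence.** The reference to these assessments could mean only grip strength and 9HPT, leaving WMFT timing unstated. A stroke-only condition x time analysis would then be possible if the WMFT were in fact repeated. This is a fair reading, and it would reduce the empty cells from 14 to 8. But nothing schedules a post-PAS WMFT, and all 8 control cells would still be empty, so the stated three-way ANOVA cannot be run on either reading.

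2. **The trial keeps its main test.** IPC is scheduled at all four time points, the hypothesis is about plasticity rather than behaviour, and the study is a pilot. It is true that the IPC analysis is not touched by this point. The loss is one of two primary measures, not both. Pilot status does not make a named primary analysis feasible.

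3. **SRTT is not a clean replacement.** Performance improves with practice, so learning can be mixed with the time effect. The sham condition answers this: the test of interest is condition x time, and practice common to both conditions does not enter it. It also stands that the document does not expressly say controls perform the SRTT (it speaks of the participant), does not name one SRTT summary, and gives no SRTT power figure. The first two must be written in. The third applies equally to WMFT time now.

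4. **The error may lie in the schedule rather than in the choice of measure.** That is possible, and the document cannot settle it. It affects which repair is right, not whether one is needed.

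**Conclusion.** The plan is wrong as written: the primary ANOVA of WMFT time cannot be run. On the natural reading at most 2 of 16 cells hold data and 6 of 7 effects are inestimable. The remaining effect is a pre-stimulation comparison that carries no information on PAS. On the reading most favourable to the plan's timing, 8 of 16 cells are empty and every group term is lost.

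The count of 2 assumes that the timing sentence covers the WMFT and that both conditions have a Pre-PAS WMFT. The conclusion that the stated model fails needs only one of two facts: no WMFT in controls, or no WMFT after PAS. The first is explicit in the contrast between the stroke-only WMFT and the tests given to both groups. The finding is confined to WMFT time and must be fixed before analysis.

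**What to change.** Reconcile the Statistical Plan with the Motor function assessment section in one of these ways, before outcome data are examined:

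- **Replace WMFT time with SRTT response time as the behavioural primary measure.** State that both groups perform the SRTT at all four time points, name the summary to be analysed (from the repeated and random sequences), and name condition x time, with its group interaction, as the effect of interest.
- **Or make IPC the sole primary measure** and list SRTT response time as secondary.

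In either case, describe WMFT time as a stroke-group baseline descriptor or covariate and remove it from the three-way ANOVA.

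If the sponsor did intend a WMFT after PAS, the assessment section must say so. The WMFT model must then be condition x time in the stroke group only, unless controls are tested as well.

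The first two options need no new participants or assessments, provided controls do perform the SRTT. They do change a primary measure, so they belong in a dated amendment, and the Power analysis should say that it does not cover SRTT. The third option adds assessments.

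A secondary matter, on which this point does not depend: if two primary measures remain, the plan needs a multiplicity rule such as Holm at an overall .05. Two independent unadjusted tests, one per measure, would give a familywise error of 1 - 0.95^2 = 0.0975.

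### No ANOVA effect is named as deciding the PAS hypothesis: for IPC the false-positive chance is about 10% to 19% over the relevant terms, and WMFT cannot carry this ANOVA as described

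*Combined protocol and SAP*

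**What the plan says.** The Statistical Plan opens with its aim: "To address the hypothesis that PAS induces LTP-like plasticity in both individuals with stroke and healthy controls". The analysis is "a three-way group (stroke, control) x condition (real PAS, sham PAS) x time", with one pre-PAS and three post-PAS time points, applied to "the primary dependent measures (IPC and WMFT time"). The decision rule is one clause: "an alpha = .05 will be used and simple effects analyses will be performed for significant interaction effects". Nothing else in the document ranks the two measures, says whether one or both must be significant, picks out a term of the ANOVA, or adjusts for multiple tests.

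The measurement sections treat the two measures differently. For the TMS-EEG recording that yields IPC, the EEG section says: "This procedure will be conducted bilaterally at each assessment timepoint (Pre-PAS, Post-PAS 0', Post-PAS 30', Post-PAS 60"). For WMFT, the Motor function assessment section says "In the stroke group, arm function will be evaluated by the Wolf Motor Function Test (WMFT") and places it, with grip strength and the peg test, "prior to completing the PAS protocol". Among the motor tests, only the serial reaction time task is scheduled at every time point.

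**The concern.** A three-factor ANOVA returns seven F tests. Without a named deciding term, a positive claim about PAS can be reached by more than one route. A condition x time effect pooled over groups, a three-way interaction followed by simple effects, or a condition main effect could each be put forward afterwards. Each is tested at .05, so the chance that at least one is significant by accident exceeds .05.

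Two further choices are left open for IPC. TMS-EEG is done on both hemispheres, but the ANOVA has no hemisphere factor. The PAS section describes traditional and cortico-cortical PAS, while the ANOVA has a single real-PAS level. At stake is whether a reported significant result can be read at its stated error rate.

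**Working it through.** **The plan's own figures.** The documents state no family-wise error rate. The nearest figures are the two sample sizes under Power analysis. Both follow from a one-sample (paired) normal formula, n = (σ(z₀.₉₇₅ + z₀.₈₀)/δ)², reading b = 0.8 as power and assuming two-sided .05, since that section gives no alpha:

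- iSP ratio: (0.11 × 2.8016 / 0.06)² = 26.38, rounded up to 27, as stated.
- Evoked response: (288 × 2.8016 / 430)² = 3.52, rounded up to 4, as stated.

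Each is sized for one comparison at .05. Neither is a term of the planned ANOVA, so this section does not reveal which term decides.

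**Inputs.** Alpha is .05 per test, unadjusted (Statistical Plan). The factors are 2 x 2 x 4 (Statistical Plan), giving 3 main effects + 3 two-way + 1 three-way = 7 tests. There are 30 participants per group (Power analysis).

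**IPC.** With k independent tests and no true effect, P(at least one significant) = 1 − 0.95^k.

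| Terms counted | k | 1 − 0.95^k | Simulated |
|---|---|---|---|
| condition x time; three-way | 2 | 9.75% | 9.8% |
| all terms containing condition | 4 | 18.5% | 18.6% |
| all terms | 7 | 30.2% | 30.1% |

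The simulation used 20,000 mixed ANOVAs under the complete null, with 30 per group, condition and time within subjects, and compound symmetry. The documents do not clearly state whether condition is within or between subjects; the formula does not depend on it.

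The three terms without condition (group, time, group x time) do not compare real PAS with sham. Two more (condition, group x condition) contain condition but average the pre-PAS value in with the post-PAS values. Only the remaining two test change over time against sham.

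**WMFT.** With no control-group data the group factor disappears. If WMFT were measured at all four time points, three terms would remain (condition, time, condition x time): 1 − 0.95³ = 14.3% (simulated 13.3%, 5,000 runs). If it is measured only before PAS, as described, only condition remains: 5%, and that test says nothing about change.

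**After the fix.** One named contrast on IPC has an error of 5%. Requiring the contrast to be significant in each group keeps the error of the both-groups claim at or below 5%. If neither group has an effect and the groups are independent, it is at most 0.05 × 0.05 = 0.25%.

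**The case against.** The strongest defence is that the intent is evident. The ANOVA is tied to one hypothesis, sham is the comparator and the time points are pre and post, so condition x time and its consistency across groups is the natural test. The plan nowhere says that any significant term would count as support. The study also calls itself a pilot, where unadjusted factorial F tests are common. This stands in part: it limits the relevant family to the terms with condition and lowers the severity. It does not name the test. Plasticity in both groups could still be argued from a pooled effect, from simple effects or from separate group results.

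A reader might infer a 30% error for each primary measure, or 51% over 14 tests (1 − 0.95¹⁴). The documents do not support either. WMFT as described cannot supply seven tests. Counting what can be run gives 7 + 3 = 10 tests (40.1%) or 7 + 1 = 8 tests (33.7%), assuming independence, and these totals still include terms that do not bear on PAS. The 30% for IPC also needs every effect to be null; if stroke and control participants truly differ in IPC, a significant group term is no false positive.

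A reader might also think that the simple effects analyses add to these rates. They are run only after a significant interaction, so under the complete null they cannot raise the chance of at least one false positive.

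**Conclusion.** The point holds in a limited form. The plan names no deciding effect and no rule for combining its two primary measures. For IPC this puts the false-positive chance at 9.75% to 18.5% over the terms that bear on PAS, about two to four times the stated .05. The 30% over all seven terms is correct arithmetic but overstates the risk to the PAS claim. These figures rest on the complete null, near-independent F tests and, for the simulation, compound symmetry.

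For WMFT the prior problem is not multiplicity. The Statistical Plan and the Motor function assessment section conflict, and WMFT should not serve as a second confirmatory measure until they are reconciled. Given the pilot status, severity is low to moderate.

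**What to change.** In the Statistical Plan, name one primary test at two-sided .05: the condition x time contrast on IPC, that is, the real-versus-sham difference in change from Pre-PAS. Comparing Pre-PAS with the mean of the three post-PAS time points is one option; the documents do not dictate it, and the sponsor should fix the choice before analysis. State which stimulated hemisphere supplies IPC and which PAS type counts as real PAS.

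A contrast pooled over groups can be significant because of one group alone. So claim plasticity in both groups only if the same contrast is significant in each group, in the same direction. No alpha split is needed for this, because both must succeed. Label all other F tests and simple effects secondary and report them with confidence intervals.

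Reconcile the Statistical Plan with the Motor function assessment section on who has WMFT and when. A Holm adjustment across IPC and WMFT is no substitute, because it would need a post-PAS WMFT change that the plan does not describe.

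For IPC the cost is wording plus the choices above. Other significant terms can no longer be presented as confirmation. The both-groups claim also has less power than the pooled test: as an illustration, with 80% power in each of two independent groups, both succeed with probability 0.8 × 0.8 = 64%.

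### The power calculations (27 and 4 subjects) concern measures and a contrast outside the primary ANOVA, so power for IPC is undemonstrated; WMFT time cannot enter that ANOVA as scheduled

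*Combined protocol and SAP*

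**What the plan says.** The Statistical Plan sets the target: "To address the hypothesis that PAS induces LTP-like plasticity in both individuals with stroke and healthy controls". The test is an ANOVA of "group (stroke, control) x condition (real PAS, sham PAS) x time", with four time points (before PAS, then 0, 30 and 60 minutes after). It "will be performed for the primary dependent measures (IPC and WMFT time"), at alpha .05.

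The Power analysis follows directly and begins "To ensure we have sufficient statistical power for our proposed aims". It gives two calculations:

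- "To detect a hemispheric difference in iSP ratio of 0.06", with SD 0.11 and b = 0.8: 27 subjects.
- "In order to measure differences in TMS-evoked EEG responses in the hemisphere opposite the site of stimulation", with mean difference 430 and SD 288 µV.msec and b = 0.8: 4 subjects.

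It then concludes: "Due to the increased measurement variability in stroke, we chose a necessary sample size of n=30/group".

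On timing, the EEG section says of the TMS-EEG recording that "This procedure will be conducted bilaterally at each assessment timepoint". The Motor function assessment section gives the WMFT to the stroke group only and places it, with grip strength and the peg test, before PAS. In that section only the SRTT is repeated at every time point.

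**The concern.** A power statement supports an analysis only if it uses that analysis's outcome and contrast. Here the outcomes and the contrast both differ. The iSP ratio is neither defined nor used elsewhere in the document. The evoked response is an amplitude area, whereas IPC is a beta-band coherence between C3 and C4. The first calculation compares hemispheres, and hemisphere is not an ANOVA factor. The second names no group, condition or time comparison. The stated input sources are standalone TMS data in chronic stroke and TMS-EEG data in young healthy people; no PAS or sham data are mentioned.

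The consequence is for interpretation. A null PAS result on IPC could be read as coming from an adequately powered study, on the strength of numbers that belong to other measures. A reader also cannot tell what size of PAS effect on IPC, or of stroke-control difference in that effect, 30 per group can detect. For WMFT time the difficulty comes before power: the schedule supplies neither a control group nor a post-PAS value.

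**Working it through.** **1. The plan's own figures.** Inputs are from the Power analysis. I read b = 0.8 as 80% power and assume two-sided alpha .05, because sidedness is not stated. The one-sample or paired normal formula is n = (1.960 + 0.842)² × (SD/difference)², and the squared sum is 7.849.

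- iSP ratio: 7.849 × (0.11/0.06)² = 26.38, so 27.
- Evoked response: 7.849 × (288/430)² = 3.52, so 4.

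Both match. The two-sample version doubles them to 52.8 and 7.04 (53 and 8 per group), which does not match. So the published numbers are one-sample or paired figures, not stroke-control comparisons. With the t distribution in place of the normal they become 29 and 6; 30 exceeds both.

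**2. Outcomes and contrasts side by side.**

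| | Power analysis | Primary ANOVA |
|---|---|---|
| Outcome | iSP ratio; evoked response (µV.msec) | IPC; WMFT time |
| Contrast | Hemisphere; response opposite the stimulated side | Group, condition, time and interactions |
| Effect size and SD for the primary outcome | None given | Needed |

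**3. What 30 per group can detect on one IPC contrast.** No effect, SD or correlation is given for IPC, so only standardized effects can be computed. Detectable effect = λ × standard-error factor, where λ is the noncentrality that gives 80% power in a two-sided .05 t test. Equal SDs, no loss and independent groups (matching not used) are assumed.

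*Condition within participants*, in SDs of each participant's real-minus-sham contrast:

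- Real versus sham, one group, n = 30, df 29: 2.899 × √(1/30) = 0.53.
- Stroke-control difference, 30 v 30, df 58: 2.849 × √(2/30) = 0.74.

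*Condition between participants*, in SDs of the participant-level change. The documents give no split, so these are assumed:

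- One group, 15 v 15, df 28: 2.902 × √(2/15) = 1.06.
- One group, 20 v 10 (two real arms pooled against sham), df 28: 2.902 × √(1/20 + 1/10) = 1.12.
- Stroke-control difference, 15/15 in each group, df 56: 2.851 × √(4/15) = 1.47.
- Stroke-control difference, 20/10 in each group, df 56: 2.851 × √(2 × (1/20 + 1/10)) = 1.56.

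The two sets use different SDs, so 0.53 and 1.06 are not on one scale. All are single-contrast figures, not power for the 3-df interaction terms.

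**4. How far power depends on what is missing.** As illustration only, borrow the iSP effect (0.06/0.11 = 0.545 SD) for the stroke-control difference in a pre/post, real/sham contrast. Take condition as within participants and one common correlation ρ, so the contrast SD is 2√(1 − ρ) single-measurement SDs. Power with 30 per group is 24% at ρ = 0.3, 31% at 0.5, 47% at 0.7, 64% at 0.8 and 91% at 0.9. Missing inputs alone can put power on either side of 80%.

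**5. The stroke-variability allowance.** For the iSP calculation, moving to 30 tolerates an SD larger by √(30/27) = 1.054, or √(30/26.38) = 1.066 from the unrounded figure: about 5% to 7%. The text states no stroke SD and no inflation factor.

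**The case against.** The strongest defence has three parts.

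First, the evoked response is not foreign to the study. It comes from the same TMS-EEG recordings as IPC, the EEG section also plans an analysis of evoked potentials, and IPC is meant to index connectivity with the opposite motor cortex. As a related measure it has some relevance. That stands, but an effect and SD in µV.msec do not transfer to a coherence.

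Second, the Research Plan calls this a pilot, and a pilot may recruit 30 per group without a power calculation. That also stands, and the fix uses it. But the plan does claim sufficiency and calls the size necessary, so the claim has to be supported or dropped.

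Third, the stroke allowance fits naturally with the figure of 4 if that figure comes from the young healthy source. This is a fair reading, so the allowance is not baseless. The plan does not say it, and gives no SD.

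A reader might go further and infer that the sums are wrong, that 53 per group are needed, or that the study is underpowered. The documents support none of these. The sums reproduce, the 53 answers a comparison that the plan never set for iSP ratio, and the true IPC effect and SD are unknown.

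**Conclusion.** The point holds as a mismatch of endpoint and analysis, not as an arithmetic error. The 27 and 4 cannot be cited as power for IPC, WMFT time or the PAS effect. Power for IPC is undemonstrated and could be adequate or not.

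In standardized terms, 30 per group detects 0.53 SD (one group) or 0.74 SD (stroke-control difference) if condition is within participants. If it is between participants, the figures are 1.06 to 1.12 and 1.47 to 1.56, in the other SD unit and under assumed splits. The PAS section leaves the choice open: it speaks of what is received at each session and also of a PAS group, and the Research Plan allows up to five sessions without settling it.

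For WMFT time, no group by condition by time power figure can exist under the current schedule. This should be fixed, but it does not call the recruitment target itself into question.

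**What to change.** 1. Withdraw the statement that power is sufficient for the aims. Present 30 per group as a pilot size, and label the iSP and evoked-response figures as not powering IPC, WMFT time or the PAS effect.
2. State whether condition is within or between participants. Name one IPC contrast, for example the change from before PAS to a named post-PAS time, real versus sham, on a named stimulated side (recording is bilateral). Give the matching detectable effect from the working, with its SD unit, and the figure for the actual split if condition is between participants. Call it a sensitivity statement for a single contrast, not power for the 3-df interactions.
3. Take WMFT time out of this ANOVA, for example by using it as a baseline descriptor in stroke, or reconcile its primary role with its assessment schedule.
4. State which calculation, and which SD, the stroke-variability allowance applies to.

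The cost is rewording of two paragraphs, a less favourable power statement, and WMFT time's place in this ANOVA. Keeping WMFT time there would instead mean added assessments in sessions planned at under 3 hours. No extra participants are needed.
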